7.1.3.3. Safety set

Safety analysis will include all subjects with signed informed consent and safety data will be presented by phase (run-in phase and study phase). Safety reporting will be done separately for the run-in period and the study phase period. Any AE and SAE occurring from the date of Visit 1 to before the date of Visit 5 will be reported as happening in the run-in phase. Any AE and SAE occurring from the date of visit 5 to the date of Visit 15 will be reported as happening in the study phase and will be reported according to the randomization arm that the subject was assigned.

For comparison of safety in the two arms, the safety set is composed of all randomized subjects, and assessed and analyzed as members of the intended randomized arm.

7.2. General Methodology

Number of enrolled patients and number of completed visits will be reported. An overview of study discontinuations will be provided. By phase (run-in phase and study phase), a description of the total number of patients screened, randomized, per study arm, and a list of reasons for failed screening, dropouts number and corresponding reasons for dropping out will be reported.

Summary statistics such as n (number of subjects), mean, standard deviation, median, minimum and maximum will be used for continuous variables. For categorical variables, summary statistics such as n, frequency counts and percentages will be used.

The templates for Tables, Listings and Figures (TLFs) will be found in the TLFs document.

7.3. Center Pooling

At all investigational centers, the same clinical investigational plan and training is followed and standardized data collection methodology and electronic case report forms (eCRF) are used. Results for the primary endpoint will be reported by center and country using a format similar to the table below. In particular, values in the sixth column (between groups difference of averages) will allow for examination of centers with outlying results. Grouping of sites based in geographies may also be reported. Available data will be used to populate the table and in case of missing data, no imputation will be performed. Centers will be pooled for analyses. No statistical test will be performed.

Country	Center	Number of patients	Treatment Arm Average (STD), of average of P1, P2 and P3 number of sensor glucose hypoglycemic events per subject per week	Control Arm Average (STD), of average of P1, P2 and P3 number of sensor glucose hypoglycemic events per subject per week	Between group difference Average of average of P1, P2 and P3 number of sensor glucose hypoglycemic events per subject per week (Treatment Arm – Control Arm)
xxxx	1	xx	xx.x (xx.xx)	xx.x (xx.xx)	xx.xx
xxxx	2	xx	xx.x (xx.xx)	xx.x (xx.xx)	xx.xx
	...				
Overall for country xxxx		xx	xx.x (xx.xx)	xx.x (xx.xx)	xx.xx
	...				
Total		xxx	xx.x (xx.xx)	xx.x (xx.xx)	xx.xx

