This study has an adaptive design. Due to the uncertainty about the hypoglycemic event rate and the magnitude of the true effect of treatment, the sample size will be re-estimated by Data Safety Monitoring Board (DSMB) in an interim assessment after a total of 60 subjects (30 treatment and 30 control group) have been randomized and followed up for 6 months. An interim analysis for sample size re-estimation will be based on the conditional power approach by Li et al. [17] and a method of by Chen et al. [18] as extended by Mehta and Pocock [19].

The interim analysis will be performed by a statistician unaffiliated with the sponsor or study statistician and member of the DSMB. Detailed instructions will be given to this statistician concerning the analysis, because it involves both the primary safety and efficacy endpoints.

The DSMB will share no data or results of analyses with the sponsor or sponsor's statistician, and present one of following messages to the sponsor after the interim analysis:

- Study has reached the futility boundary and it is recommended to be terminated for futility.
- Continue the study to its conclusion without modification of sample size or inclusion criteria.
- Increase the numbers of patients in each treatment group.
- Revise the inclusion criteria.

The statistician will prepare and save a report of the interim analysis. This report will be sent to the sponsor on completion of the study.

C.6 Randomization

The randomization will follow a block randomization with blocks of different sizes. At site level, the order of the block sizes will be selected randomly and a random 1:1 treatment allocation will be performed within each block.

Investigators will be blinded to the number and size of the blocks.

Randomization will be performed via the electronic CRF.

In case technical issues occur with the electronic CRF (i.e. Internet access, system maintenance), a randomization list will be generated for each site by the statistician and the statistician will be able to communicate the randomization arm to the study team and site staff.

C.7 Sample size

The sample size calculation was performed based on assumptions from the results from the *ASPIRE* study [3]. In particular, the mean number of sensor glucose hypoglycemic events below or equal to 55 mg/dL (3.0 mmol/L) per patient/week is expected to be 2 in the arm with CSII with MiniMed 640G alone (control group) and standard deviation of 1.56.

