- Review subject therapy and make adjustments, per investigator judgment
- Review SMBG/Bolus Wizard use
- Review adverse event or device deficiency, if any
- Dispense supplies for 6 weeks:
 - 10 Enlite sensors (2 box of 5)
 - 350 Strips
 - 20 Infusion sets (2 box of 10)
 - 20 Reservoirs (2 box of 10)
 - 4 AA batteries (1 pack of 4)
- Plan next call with subject in 4 weeks.

Visit 9 Data collection

- Visit 9 eCRF
- CareLink clinical data upload
- Subjects Products Tracking log eCRF
- Adverse Event or Device Deficiency eCRF, if applicable.

Visit 9 Procedures Control Arm:**6 week Follow-up Visit**

Subject will come to the site

Study staff will:

- Upload the MiniMed 640G into CareLink Clinical. Use correct Subject ID (311-XXX-XXX).
- Review subject therapy and make adjustments, per investigator judgment
- Review SMBG/Bolus Wizard use
- Review adverse event or device deficiency, if any
- Provide a refresher training on sensor insertion, replacement and blinded recording with the GST3C transmitter.
- Dispense supplies for 6 weeks:
 - 2 GST3C transmitter (1 back-up)
 - 1 GST3C charger
 - 1 GST3C watertight tester
 - 1 Enlite One-Press serter
 - 4 Enlite sensors (2 back-up)
 - 350 Strips
 - 20 Infusion sets (2 box of 10)
 - 20 Reservoirs (2 box of 10)
 - 4 AA batteries (1 pack of 4)
- Plan next call with subject in 4 weeks.

Visit 9 Data collection

- Visit 9 eCRF
- CareLink clinical data upload
- Subjects Products Tracking log eCRF
- Adverse Event or Device Deficiency eCRF, if applicable.

F.3.10 Visit 10: 10 week Follow-Up Call [Visit 6 + 70 days (±7 days max)]**Visit 10 Procedures Treatment Arm:****10 week Follow-Up Call**

Study staff will call the subject to:

- Review MiniMed 640G and sensor use.
- Review SMBG/Bolus Wizard use.
- Review adverse event or device deficiency, if any.
- Plan next visit with subject in 2 weeks.

Visit 10 Procedures Control Arm:**10 week Follow-Up Call**

Study staff will call the subject to:

- Review MiniMed 640G use.
- Review SMBG/Bolus Wizard use.
- Ensure blinded GST3C transmitter recording is started adequately with proper sensor insertion, and will be continued until next clinic visit.
- Remind subject to replace the sensor after maximum 7 days of wear.
- Review adverse event or device deficiency, if any.
- Plan next visit with subject in 2 weeks.

Visit 10 Data collection:

- Visit 10 eCRF
- Adverse Event or Device Deficiency eCRF, if applicable.

Visit 10 Data collection

- Visit 10 eCRF

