6.2. Sample size

The sample size calculation was performed based on assumptions from the results of the *ASPIRE study* (Bergenstal, et al., 2013). In particular, the mean number of sensor glucose hypoglycemic events below or equal to 55 mg/dL (3.0 mmol/L) per subject/week is expected to be 2 with standard deviation of 1.65 in the Control arm (CSII therapy alone with MiniMed 640G).

Assuming a two-sided two-sample t-test, alpha=0.05, power=80% and 40% reduction in the mean number of sensor glucose hypoglycemic events per subject/week in the Treatment arm (SAP with MiniMed 640G and SmartGuard), as compared to the control arm, the required sample size is 136 subjects (68 in each arm) completing the 6 month follow up of the study phase.

The dropout rate during the 6-month follow-up after randomization has been estimated to be around 15%. Incorporating this dropout rate, a total of 160 subjects will be randomized in a 1:1 ratio either to the SAP therapy arm (MiniMed 640G with SmartGuard) or to the CSII therapy arm (MiniMed 640G).

7. Statistical Methods

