7.6. Demographic and Other Baseline Characteristics

A summary of basic subject demographics and baseline characteristics will be included in the study report using appropriate summary statistics (n, mean, standard deviation, median, minimum and maximum for continuous variables; n, frequency counts and percentages for categorical variables).

Baseline data will be obtained from visit 2 (CRF: demographics, medical history, HbA1c, Creatinine, Clark and Gold score) and visit 5 (baseline sensor data: CareLink clinical upload).

Although this is a randomized trial, there may be baseline differences between the two groups just by chance. Baseline characteristics for all patients and by treatment group will be reported.

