7.9. Evaluation of Objectives

7.9.1. Analysis of primary endpoint

A sensor hypoglycemic event is defined as sensor glucose values less or equal to 55 mg/dL (3.0 mmol/L) for more than 20 consecutive minutes. When the time between two successive events is less than 30 minutes, they will be combined and counted as one event.

The primary endpoint is the mean number of sensor glucose hypoglycemic events (MNSHE) per subject per week computed using the sensor data collected during each of the 3 periods of 2 weeks. As described in section 7.7.2, the last 4032 sensor readings from each period are used for analysis.

The goal is to compare the MNSHE per week in the two study arms. The between group difference in MNSHE for the overall at 3, 4.5 and 6 months (using Periods 1, 2 and 3) is of primary interest and will be compared using the following hypotheses:

Null-hypothesis: $H_0: MNSHE_{TREATMENT} = MNSHE_{CONTROL}$

Alternative hypothesis: $H_A: MNSHE_{TREATMENT} < MNSHE_{CONTROL}$

The null-hypothesis will be rejected in favor of the alternative hypothesis if the mean of the estimated regression coefficient β_2, β_4 and β_6 is <0 and the associated p-value for this contrast is less than 0.05 using the mixed model:

$$MNSHE_{ij} = (\beta_1 + \beta_2 * group_i) * period1 + \\ (\beta_3 + \beta_4 * group_i) * period2 + \\ (\beta_5 + \beta_6 * group_i) * period3 + \beta_7 * BLMNSHE_i + b_{0i} + \epsilon_{ij}$$

Where:

$MNSHE_{ij}$ is the mean number of sensor glucose hypoglycemic events per week for subject i at period $j=1, 2$ or 3 , $BLMNSHE_i$ is the baseline mean number of sensor glucose hypoglycemic events per week for subject I , and b_{0i} are random effects.

If period = 3 months, then period1= 1, 0 otherwise

If period = 4.5 months, then period2=1, 0 otherwise

If period = 6 months, then period3=1, 0 otherwise

If arm=Treatment, then group=1, 0 otherwise

In case of partially missing baseline mean number of sensor glucose hypoglycemic events (BLMNSHE), the method proposed by White and Thompson will be use (Adjusting for partially missing baseline measurements in randomized trials, 2005, Statistics in Medicine).

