7.9.2. Analysis of secondary endpoints

The blinded (for the control arm) or unblinded (for the treatment arm) sensor data collected during the 3 periods of 2 weeks will be used. Difference between the treatment arm and the control arm will be analyzed in a similar way as the primary endpoint using a random effects model when hypothesis testing may be performed. If

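### Low-priority efficiency point: randomisation is blocked within site but the primary model has no site term, so the primary confidence interval is slightly too wide if sites differ after baseline adjustment

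*SAP*

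**What the plan says.** Protocol C.6 makes site, in effect, a stratification factor: "At site level, the order of the block sizes will be selected randomly", and "a random 1:1 treatment allocation will be performed within each block".

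SAP 7.3 says "Centers will be pooled for analyses". It adds a table of the primary endpoint by center and country, which is descriptive and untested.

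The primary model in SAP 7.9.1 contains period, arm by period, a subject random effect and one covariate, BLMNSHE, which "is the baseline mean number of sensor glucose hypoglycemic events per week for subject I". It has no site or country term. SAP 7.6 takes the sensor baseline from "visit 5 (baseline sensor data: CareLink clinical upload", that is, from the run-in.

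SAP 7.9.2 has the secondary endpoints "analyzed in a similar way as the primary endpoint using a random effects model", so those models share the omission. No other section adds site or plans a site-adjusted sensitivity analysis, and SAP 7.12 does not mention it.

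**The concern.** When allocation is balanced within site, differences between sites in event rate largely cancel out of the arm comparison, so the true variance of the estimated difference does not contain them. A model that ignores site leaves them in its error term and reports too large a standard error.

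The baseline covariate removes part of any site difference already present at run-in. It cannot remove differences that arise later. These are possible in both arms, because at Visits 9, 11 and 13 (Protocol F.3.9, F.3.11, F.3.13) staff are to "Review subject therapy and make adjustments, per investigator judgment".

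What is at stake is precision only: a slightly wide interval and a slightly conservative test. The planned power is not undercut, because SAP 6.2 sized the trial without any adjustment: "Assuming a two-sided two-sample t-test, alpha=0.05, power=80% and 40% reduction". The secondary tests in SAP 7.5 form a sequence that stops at the first non-rejection. The loss there cannot be computed, because the documents give no SD or effect for those endpoints.

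**Working it through.** **Inputs from the documents.** Control mean 2, SD 1.65, 40% reduction (difference 0.8 events/week), two-sided alpha 0.05, power 80%, 15% dropout, 160 randomised 1:1 (SAP 6.2); up to 25 sites (Protocol C.4).

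**The plan's own figure.** A two-sided two-sample t-test with difference 0.8 and SD 1.65 needs 68 per arm, 136 in all (power 80.1%), and 136/0.85 = 160. This reproduces SAP 6.2. Protocol C.7 gives SD 1.56, which leads to 61 per arm and does not reproduce 136, so 1.65 is used here.

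**Assumptions.** The documents do not give these: correlation r = 0.5 between baseline and follow-up, blocks of 2 and 4, and a site ICC (the site share of follow-up variance before baseline adjustment) of 0, 0.05 or 0.10.

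**Site share left after baseline adjustment.**
- Differences already present at run-in: ICC(1 − r)/(1 + r). For 0.05: 0.05 × 0.5/1.5 = 0.017. For 0.10: 0.033.
- Differences arising after run-in: ICC/(1 − r²). For 0.05: 0.05/0.75 = 0.067. For 0.10: 0.133.

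**Ceiling on the overstatement.** With perfect balance within site, the standard error is too large by the factor 1/√(1 − residual ICC). At 0.067 that is 3.5%, and at 0.133 it is 7.4%. Small sites, incomplete blocks and dropout make the balance imperfect, so the actual figure is lower.

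**Check of the interval without site.** Residual SD = 1.65 × √(1 − 0.25) = 1.429. SE = 1.429 × √(2/68) = 0.245. Half-width = 1.978 × 0.245 = 0.485.

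**Simulation.** The subject average of the three periods was regressed on arm and baseline, without site and with a random site intercept (variance estimated by REML, zero allowed, residual degrees of freedom). There were 32,000 null trials per setting (Monte Carlo error about 0.12 points) and 16,000 under the alternative (about 0.2 points).

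| Setting | SE overstated | Type I error, without / with site | Power, without / with site |
|---|---|---|---|
| ICC 0 | none | 5.0% / 5.2% | 89.5% / 89.8% |
| Present at run-in, ICC 0.05 or 0.10 | about 1% | 4.7% / 5.0–5.2% | gain about 0.4 points |
| Arising later, ICC 0.05 | about 2.4% | 4.4% / 5.0% | 90.2% / 91.2% |
| Arising later, ICC 0.10 | about 4.9% | 3.9% / 5.0% | 91.2% / 93.0% |

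In the last row the 95% CI half-width falls from 0.485 to 0.457 events/week. Blocks of 4 and 6, or 18 sites, gave similar results. A smaller repeat (5,000 trials per setting) agreed, except that it put the overstatement at later-arising ICC 0.05 at 1.3% to 1.5%; the Monte Carlo error on that ratio is about 1 point.

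**Second parametrisation.** Here the residual SD after baseline is kept at 1.65, ICC is the share of that residual variance, and the ICC is treated as known, which is a best case. With 25 sites, the interval without site relative to the random-site interval is 1.00, 1.01, 1.02, 1.04 and 1.10 times as wide at ICC 0, 0.02, 0.05, 0.10 and 0.20. Power at ICC 0.10 is 79.5% without and 81.5% with site; it is near 80% because baseline earns no credit. Across 16 and 25 sites, coverage without site was 94.8% to 97.0%.

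**Fixed or random site effects.** In the same runs with 25 sites, fixed site effects gave a full interval width of 1.156 against 1.123 with no site term at ICC 0, and 1.128 against 1.123 at ICC 0.05. They became narrower only by ICC 0.10 (1.100 against 1.123). A random intercept avoids that loss.

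**The case against.** The strongest reply is that nothing is wrong with the inference. The test is valid and the power is ample. The premise that sites differ after baseline adjustment is also not in the documents.

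The larger effect needs differences that appear only after run-in, and the protocol works against these. It sets common glucose targets for all subjects (F.2.2) and a minimum site size meant to limit differences in practice (C.8). SAP 7.3 cites a common plan, training and data collection. If patients were already in their site's care, most practice differences would show at run-in, where the effect is about 1%. This stands, and it is why the size is stated as conditional.

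The power gains also need careful reading. The gain of about 0.4 points in the run-in setting is no larger than the 0.3 points seen at ICC 0, so it is noise. When both models were compared at equal type I error (6,000 trials per setting), no power gain was detectable, even for later-arising ICC 0.10 (92.3% against 92.4%). The point estimate is about equally precise either way (empirical SD 0.2325 against 0.2322 in one run). What site adds is a correctly calibrated standard error and interval, not a better estimate.

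Two practical points also stand. The simulations used subject averages with residual degrees of freedom, not the three-period model with Kenward-Roger recommended below. The interim re-estimation sits in a separate committee plan, against which any change to the primary model must be checked.

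None of this removes the mismatch between design and analysis. The by-center table does not address it, because it leaves the primary standard error unchanged.

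**Conclusion.** The concern holds as a low-priority efficiency point. Allocation is blocked by site, the primary model ignores site, and no site-adjusted analysis is planned. If sites differ after baseline adjustment, the primary interval is wider than the design warrants and the type I error falls below 5%. Under the stated assumptions the standard error is overstated by nothing at ICC 0, by about 1% if site differences exist at run-in, and by about 5% if they arise later with an ICC of 0.10. The result rests on an assumed r of 0.5, assumed block sizes and an assumed ICC. Confidence in the size is moderate; the direction, towards conservatism, is clear.

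**What to change.** In SAP 7.9.1, pre-specify a random intercept for site, with the subject random effect nested within site and Kenward-Roger degrees of freedom. Do not use fixed effects for up to 25 small sites. Carry the same term into the secondary models tested under SAP 7.5. In SAP 7.3, replace "Centers will be pooled for analyses" by a sentence such as: *All centers are analysed together, with center as a random intercept.* Keep the by-center table descriptive. If the primary model is not to be changed, pre-specify the site model as a sensitivity analysis.

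The cost is one extra RANDOM statement in PROC MIXED and one or two SAP sentences, fixed before the final data are analysed, with no new data. The change must be carried into the independent programming of the primary endpoint (SAP 8) and, if it is made to the primary model, checked against the interim plan. If the site variance is estimated as zero, the model reduces to the current one, apart from the degrees-of-freedom method, which the SAP does not state at present.

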7.4. Handling of Missing Data and Dropouts

Efficacy analyses of the primary endpoint will be performed in the Intent to Treat (ITT) basis. The analysis will be based on a repeated measures random effects model (section 7.9.1) with PROC MIXED that uses all available data and accounts for possible missing at random data.

Efficacy analysis of other secondary endpoints where hypothesis testing may be performed will use random mixed models. For exploratory analysis of other endpoints without hypothesis testing, available data without imputation of missing values will be used.

In case of dates collected at baseline with missing day and/or month the next procedure will be applied. A missing month will be imputed using the month 'July' and a missing day will be imputed with the day '15'. This applies only to dates related to medical history and baseline information with missing month and/or day.

For tables and listings of safety data a conservative/worst case scenario approach will be taken in case of partially missing dates. For date of discharge with missing day, the day will be set to last day of that month. For date of admission with missing day, the day will be set to first day of that month. If that is before day of start of study phase (within the same month), then day will be set equal to day of start of study phase. And if it is before day of start of run-in, then it will be set to day of start of run-in. Thus, duration is set to be as long as possible and by preference after intervention.

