7.10. Safety Evaluation

Safety analysis will include Number of severe hypoglycemic events, diabetic ketoacidosis events, (Serious) Adverse Events, (Serious) Adverse Device Effects and Device Deficiencies.

Analysis will include: hypoglycemia-related number and mean duration of hospitalizations, number and mean duration ICU (intensive care unit) care, number of emergency room admissions, number of events requiring ambulance assistance and number of lost days from school or work.

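### The SAP 7.4 rule for a missing admission day ignores a known discharge date, so it can date a run-in hospital stay as starting after it ended

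*SAP*

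**What the plan says.** SAP 7.4 handles partly missing dates in the safety tables and listings, and describes its approach as conservative. It treats the two ends of a hospital stay separately.

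- Discharge: "For date of discharge with missing day, the day will be set to last day of that month".
- Admission: "For date of admission with missing day, the day will be set to first day of that month".
- Shift to the study phase: if the imputed admission is "before day of start of study phase (within the same month), then day will be set equal to day of start of study phase".
- Floor: "And if it is before day of start of run-in, then it will be set to day of start of run-in".
- Stated aim: "Thus, duration is set to be as long as possible and by preference after intervention".

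SAP 7.1.3.3 splits safety reporting by phase. An AE or SAE "occurring from the date of Visit 1 to before the date of Visit 5 will be reported as happening in the run-in phase"; from the date of Visit 5 onward, events are reported by randomised arm.

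The imputed dates feed a planned output. SAP 7.10 lists "hypoglycemia-related number and mean duration of hospitalizations, number and mean duration ICU (intensive care unit) care", which Protocol C.2.3 places among the tertiary, descriptive endpoints.

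**The concern.** The shift to the study-phase start has one condition, that both dates lie in the same calendar month. No sentence compares the shifted admission with a discharge date that is already on record. When that discharge is before the study-phase start, the record itself shows that the stay ended in run-in, yet the rule dates its beginning after randomisation.

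Two things are at stake. The first is an impossible value: a negative length of stay in a table of means, which shortens the mean although the rule aims for the longest duration. The second is phase. A stay known to be over before randomisation carries a study-phase admission date, and a program that assigns phase from that date would report it under an arm. If the plan does not settle this, someone has to decide what to do with the record after the allocation is known, in an open-label trial.

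**Working it through.** The documents give no figure on this point to reproduce. The check applies the sentences of SAP 7.4 literally, with the study phase starting at Visit 5 as in SAP 7.1.3.3. The calendar dates below are assumed for illustration.

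**Example 1.** Study phase starts 20 March; admission in March, day missing; discharge 10 March, known.

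- First-of-month rule: admission = 1 March.
- 1 March is before 20 March in the same month, so admission = 20 March.
- The run-in floor does not apply, because 20 March is after the run-in start.
- Duration = 10 − 20 = −10 days, and the admission is dated in the study phase.

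**Example 2.** Run-in starts 2 March; Visit 5 on 20 March; true stay 8 to 11 March; admission day missing; discharge known.

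- Literal rule: admission = 20 March; duration = 11 − 20 = −9 days, against a true 11 − 8 = 3 days.
- With the shift skipped because the known discharge precedes Visit 5: admission = 1 March, raised to 2 March by the run-in floor; duration = 11 − 2 = 9 days, and the stay remains in run-in. This is still the longest stay consistent with the record, as the plan intends.

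**When it happens.** For discharge day D and study-phase start day S in the same month, the rule gives D − S, which is negative whenever D is before S. So it strikes every completed run-in stay that has a missing admission day, an admission in the calendar month of the study-phase start, and a known discharge before that start. Stays admitted on or after the study-phase start are not reversed: none was in a run over every Visit 5 date in a 365-day year.

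**How much of run-in is exposed.** Protocol F.3.4 and F.3.5 put Visit 4 at 7 to 10 days after Visit 3, and Visit 5 at 7 to 14 days after Visit 4. Visit 3 to Visit 5 therefore takes 14 to 24 days. The 7 days allowed between Visits 2 and 3 (F.3.3) bring this to 24 + 7 = 31. Assume admissions spread evenly over run-in and over the year. An admission g days before Visit 5 then falls in the same calendar month with probability of about 1 − 12g/365. For 3-day stays completed before Visit 5:

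| Run-in (days) | Range of g | Mean g | Share reversed |
|---|---|---|---|
| 14 | 4 to 14 | 9 | 1 − 108/365 = 70% |
| 24 | 4 to 24 | 14 | 1 − 168/365 = 54% |
| 31 | 4 to 31 | 17.5 | 1 − 210/365 = 43% (rounded up; full count 42.6%) |

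Over stays of 1 to 5 days the full count ranges from 39% to 74%. These are shares of completed run-in stays that already have a missing admission day and a known discharge. They are not shares of all hospital stays.

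**Effect on a mean.** Replacing a true +3 days by −9 lowers the mean of k stays by 12/k days: 4.0 for k = 3, 2.4 for k = 5, 1.2 for k = 10. The values of k are assumed.

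**Phase.** SAP 7.1.3.3 classifies by when the AE occurs, and Protocol F.6.3 collects the date of the event as its own item. SAP 7.4 gives no rule for a partly missing event date and does not say which date sets the phase of a stay. With a recorded onset of 8 March, Example 2 would show onset 8 March, admission 20 March and discharge 11 March. If phase follows onset, the stay is in run-in; if it follows the imputed admission, it is in an arm. The duration is impossible either way.

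**The case against.** The strongest reply is that the trigger is remote. It needs a hospital stay in a run-in of a few weeks, a missing admission day, a known discharge day, the same calendar month as the study-phase start, and a discharge before it. Hospitalisation for serious deterioration is an SAE, which must be reported immediately (Protocol F.6.5, Table 6), is reviewed by the CEC (F.6.6) and is subject to data queries (G.1.3). SAP section 8 requires at least code review, with simple checks where appropriate. A negative stay would probably be noticed. All of that stands and keeps the point small. It does not repair the rule, because noticing the value still leaves no pre-specified way to resolve it.

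A reader might also infer three stronger things, which the documents do not support.

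- *That pre-randomisation stays are charged to an arm in breach of SAP 7.1.3.3.* This follows only if phase is taken from the imputed admission date. The SAP does not say so, and a separate event date is collected.
- *That the rule contradicts its own aim, because moving an admission forward can shorten a stay.* With both days missing in March, Example 2 would run from 20 to 31 March, 11 days, instead of 31 − 2 = 29 days from the run-in start. But the aim has two parts, the second being a preference for dates after intervention, and one part may limit the other.
- *That turning a short stay into about a month is an error that biases the arms.* Lengthening is a declared worst-case choice applied alike in both arms. Nothing in the documents suggests that incomplete dates will be commoner in one arm. Means from complete dates only would be a trade-off, since they discard stays.

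**Conclusion.** The point holds as a narrow defect: a stated rule gives an impossible result, with admission after a known discharge, for an identifiable set of run-in stays. It also gives those stays a study-phase date. Reporting them by arm is conditional on how phase is derived.

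The conclusion rests on a literal reading of SAP 7.4 and on Visit 5 as the study-phase start. SAP 7.1.1 counts Visit 5 itself as run-in, and treatment starts at Visit 6. A later start would move the imputed admission later still, so the finding does not depend on that choice.

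The consequence is minor. It reaches only the descriptive tables and listings of hospital and ICU stays. These durations are outside the testing hierarchy in SAP 7.5, and the primary analysis is untouched. The frequency cannot be derived, because the documents do not say how often days will be missing or how many hospital stays are expected.

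**What to change.** Add to SAP 7.4:

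1. An imputed admission date may not be later than a known discharge date and may not contradict a recorded event onset date.
2. The shift to the study-phase start is not applied when the known discharge or the recorded onset is before that start; the stay then remains in run-in.

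The cost is two sentences and one programming check. No stay leaves the counts, and the worst-case lengthening stays as declared. Optionally, state beside each mean duration how many stays had an imputed date, so that a reader can see how far the mean depends on the rule.
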